### 8.3.1. Clinical Safety Laboratory Assessments

- The investigator must review the laboratory report, document this review, and record any clinically significant changes occurring during the study as an AE. The laboratory reports must be filed with the source documents.
- Abnormal laboratory findings associated with the underlying disease are not considered clinically significant unless judged by the investigator to be more severe than expected for the subject's condition.
- All laboratory tests with values considered clinically significantly abnormal during participation in the study or after the last dose of IMP should be repeated until the values return to normal or baseline or are no longer considered clinically significant by the investigator or Sponsor's Medical Monitor.
  - If clinically significant values do not return to normal / baseline within a time judged reasonable by the investigator, the etiology should be identified, and the Sponsor notified.
  - All protocol-required laboratory tests must be conducted in accordance with the laboratory manual and the Schedule of Activities (Section 1.3).
  - If laboratory values from nonprotocol-specified laboratory tests performed at the institution's local laboratory require a change in subject management or are considered clinically significant by the investigator (eg, SAE or AE or dose modification), then the results must be recorded in the subject's source documents.

## 8.4. Adverse Events, Serious Adverse Events, and Other Safety Events

AEs and SAEs are defined in Section 10.2.1.

No AEs of special interest are defined for this study.

The investigator and any qualified delegates are responsible for detecting, documenting, and recording events that meet the definition of an AE or SAE and remain responsible for following up.

The methods of reporting, recording, evaluating, and assessing causality of AEs, SAEs, and other significant AEs and the procedures for completing and transmitting SAE reports are provided in Section 10.2.

## 8.5. Pharmacokinetics

Blood samples for IgG level determination will be collected pre-dose at baseline and study visits indicated in the Schedule of Activities (Section 1.3).

Additional blood samples for IgG levels will be collected in a subset of subjects (N = approximately 25) during the Open-label Treatment Period for serial PK sampling starting at Week 41. The additional samples will be collected at the following time points:

- Week 41, Day 2 (24 h  $\pm$  3 h after the start of Day 1 infusion)
- Week 41, Day 3 (48 h  $\pm$  3 h after the start of Day 1 infusion)
- Week 41, Day 4 (72 h  $\pm$  3 h after the start of Day 1 infusion)
- Week 41, Day 6 (120 h  $\pm$  3 h after the start of Day 1 infusion)

The samples for total serum IgG concentrations will be analyzed by a centralized bioanalytical laboratory. IgG concentrations during the Double-blind Treatment Period will not be disclosed prior to unblinding.

## 8.6. Biomarkers

### 8.6.1. Autoantibodies and Disease Biomarkers in Blood

Blood samples (serum /plasma) will be collected for the measurement of autoantibodies and disease biomarkers (eg, cytokines) that may be related to post-COVID POTS and will be assessed to determine baseline cytokine levels as well as proportion of autoantibody-positive subjects. Additional samples will be collected post-treatment as indicated in the Schedule of Activities (Section 1.3) to determine change from baseline, and to assess the relationship between change from baseline and efficacy.

The assessments of disease biomarkers may include, but are not limited to, the following: alpha 1 adrenergic receptor antibody, muscarinic receptor antibody, and anti-nuclear antibodies. Autoantibodies and disease biomarkers, including additional markers of proinflammatory response (eg, IL-6, IL-8 and other cytokines previously described as elevated in POTS) may be measured as exploratory research analysis, and will be included in an exploratory biomarker report, but will not be included in the clinical study report.

Blood samples for autoantibody and cytokine assessment are collected at the time points specified in the Schedule of Activities (Section 1.3).

Samples may be retained for up to 15 years and then destroyed.

### 8.6.2. Optional Blood Transcriptomics Analysis

In subjects who consent, whole blood samples will be collected and stored for RNA sequencing and transcriptomic analysis of changes in inflammatory pathways in peripheral blood and potential biomarkers of treatment response, disease activity, comorbid conditions and safety. The results of RNA transcriptomics analysis will be part of an exploratory research analysis and will be included in an exploratory biomarker report, which will not be included in the clinical study report.

**8.6.3. Optional Future Research**

Subjects may optionally consent for future research samples (blood) and residual samples (including PK) to be used for future research. Such research is directed at better understanding disease and the activity and interaction of IgPro20 with related molecular pathways, drug pharmacology, insight into the mechanisms of AEs, and the discovery of new therapeutic targets. Samples may also be used to facilitate biomarker innovation, developing new testing methodology and statistical analysis. Samples may be retained for up to 15 years and then destroyed.

**8.7. Genomics**

Genomics will not be evaluated in this study.

**8.8. Immunogenicity Assessments**

Immunogenicity will not be evaluated in this study.

**8.9. Medical Resource Utilization and Health Economics**

Medical resource utilization and health economics will not be evaluated in this study.

## 9. STATISTICAL CONSIDERATIONS

### 9.1. Statistical Hypotheses

The study is designed to test the null ( $H_{01}$ ) versus the alternative ( $H_{11}$ ) hypothesis of the primary endpoint for the proportion of subjects no longer meeting diagnostic criteria of post-COVID POTS as measured by standardized standing test (ie, no longer experiencing HR increase of  $\geq 30$  bpm, in the absence of orthostatic hypotension [ie, sustained 20 mmHg decrease of SBP]) at the end of the Double-blind Treatment Period.

$$H_{01}: P_{\text{IgPro20}} \leq P_{\text{Placebo}} \quad \text{versus}$$

$$H_{11}: P_{\text{IgPro20}} > P_{\text{Placebo}}$$

Where  $P_{\text{IgPro20}}$  and  $P_{\text{Placebo}}$  indicate the proportion of subjects no longer meeting diagnostic criteria of post-COVID POTS as measured by standardized standing test in the IgPro20 and placebo group, respectively. The test for superiority will be performed at a 1-sided alpha level of 2.5% using a Farrington-Manning test.

Hypothesis for the key secondary endpoints are:

$$H_{02}: \mu_{\text{IgPro20}} \geq \mu_{\text{Placebo}} \quad \text{versus}$$

$$H_{12}: \mu_{\text{IgPro20}} < \mu_{\text{Placebo}}$$

Where,  $\mu_{\text{IgPro20}}$  and  $\mu_{\text{Placebo}}$  correspond to the treatment group means of interindividual changes in OI score of COMPASS-31 for IgPro20 and placebo, respectively. The test for superiority will be performed using a  $t$ -test.

$$H_{03}: \mu_{\text{IgPro20}} \geq \mu_{\text{Placebo}} \quad \text{versus}$$

$$H_{13}: \mu_{\text{IgPro20}} < \mu_{\text{Placebo}}$$

Where  $\mu_{\text{IgPro20}}$  and  $\mu_{\text{Placebo}}$  correspond to the treatment group means of interindividual changes in COMPASS-31 total score for IgPro20 and placebo, respectively. The test for superiority will be performed using a  $t$ -test.

$$H_{04}: \mu_{\text{IgPro20}} \geq \mu_{\text{Placebo}} \quad \text{versus}$$

$$H_{14}: \mu_{\text{IgPro20}} < \mu_{\text{Placebo}}$$

Where  $\mu_{\text{IgPro20}}$  and  $\mu_{\text{Placebo}}$  correspond to the treatment group means of interindividual changes in HR for IgPro20 and placebo, respectively. The test for superiority will be performed using a  $t$ -test.

Testing will be performed accounting for multiplicity as outlined in Section 9.4.3 to preserve the alpha level of 2.5%.

### 9.2. Sample Size Determination

Based on the rationale presented in Section 4.3, assuming the proportion of subjects no longer meeting diagnostic criteria of post-COVID POTS as measured by standardized standing test at the end of the Double-blind Treatment Period. Sample size assumptions are based on the 30% and 60% response for the placebo and IgPro20 group, respectively; under

these assumptions, at least 126 subjects will be required to provide 90% power (2:1 randomization) to detect a 30% difference in proportion of responders using a Farrington-Manning test for a 1-sided alpha of 2.5%. An additional 18 subjects will be randomized to account for a futility analysis at 54 subjects, and an additional 33 subjects will be randomized to ensure > 100 subjects treated with IgPro20 for >1 year will be achieved considering approximately 20% early drop out. Therefore, the final number of patients to be randomized is 177 (118:59).

For hypothesis testing, an alpha of 2.5% (1-sided) will be used. Randomization will be continued if the dropout rate is over 10%.

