  - Positive confirmatory standardized standing test (ie, HR increase of  $\geq 30$  bpm [ $\geq 40$  bpm for subjects aged 18 to 19 years] within 10 minutes in the absence of orthostatic hypotension) at the Screening visit
  - According to the investigator's judgment, the subject (or the subject's legally acceptable representative[s]) understands the nature, scope, and possible consequences of the study
  - Subject is capable of reading, understanding, and completing questions / assessments in an electronic clinical outcomes assessment (eCOA) solution
  - Subject is willing to complete 52 weeks of SC infusions

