4.5. Determination of the Sample Size

Assuming the proportion of subjects no longer meeting diagnostic criteria of post-COVID POTS as measured by standardized standing test at the end of the Double-blind Treatment Period is 30% and 60% for the placebo and IgPro20 group, respectively, at least 126 subjects will be required to provide 90% power (2:1 randomization) to detect a 30% difference in proportion of responders using a Farrington-Manning test for a 1-sided alpha of 2.5%. An additional 18 subjects will be randomized to account for a futility analysis at 54 subjects, and an additional 33 will be randomized to ensure > 100 subjects treated with Hizentra for >1 year will be achieved considering approximately 20% early drop out. Therefore, the final number of subjects to be randomized is 177 (118:59).

For hypothesis testing, an alpha of 2.5% (1-sided) will be used. Randomization will be continued if the dropout rate is over 10%.

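### At the plan's own 20% dropout, the 118 IgPro20 subjects in the 177 target leave about 94 with long-term exposure, not more than 100

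*Protocol*

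**What the plan says.** Protocol 9.2 builds the sample size in three steps.

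- **Power.** "Sample size assumptions are based on the 30% and 60% response for the placebo and IgPro20 group, respectively"; with 90% power, one-sided alpha of 2.5% and 2:1 allocation, this gives 126 subjects.
- **Futility analysis.** "An additional 18 subjects will be randomized to account for a futility analysis at 54 subjects", which brings the total to 144.
- **Exposure.** A further 33 are added to "ensure > 100 subjects treated with IgPro20 for >1 year will be achieved considering approximately 20% early drop out", which brings the total to 177, split 118:59.

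The synopsis (Protocol 1.1, Statistical Methods) gives the same exposure reason. SAP 4.5 repeats it with the brand name: "ensure > 100 subjects treated with Hizentra for >1 year will be achieved considering approximately 20% early drop out". No other reason is given for the last 33 subjects.

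Protocol 9.2 then says that randomization goes on if dropout is above 10%. Protocol 2.2 and SAP 4.5 say the same. Protocol 7.4 says that withdrawn subjects are not replaced.

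On duration, Protocol 4.1 sets 24 double-blind weeks and 28 open-label weeks. Inclusion criteria in Protocol 5.1 include "Subject is willing to complete 52 weeks of SC infusions". SAP 7.1 ends the open-label period at the end of Week 52.

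**The concern.** The sentence names a target (more than 100 subjects), a dropout rate (about 20%) and an arm size (118), and these three figures do not agree. The exposure count is the whole stated reason for going from 144 to 177. A reader who relies on the sentence would believe that the long-term safety database is protected against 20% dropout, when under that assumption the target would most likely be missed. The duration wording adds a smaller mismatch, because the planned course is 52 weeks and not longer than a year.

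**Working it through.** **Inputs.** Response rates of 30% and 60%, 90% power, one-sided alpha of 2.5%, 2:1 allocation, add-ons of 18 and 33, final split 118:59, dropout of about 20% and a target above 100 (Protocol 9.2, SAP 4.5). Periods of 24 and 28 weeks (Protocol 4.1). Placebo subjects move to IgPro20 at Week 25 (Protocol 1.3.2, footnote a; SAP 4.3).

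**1. The plan's own figures reproduce.** At a zero margin the Farrington-Manning test uses the pooled variance. The pooled rate is (0.30 + 2 × 0.60)/3 = 0.50. The placebo group size is

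n = [1.960 × √(0.50 × 0.50 × 1.5) + 1.282 × √(0.30 × 0.70 + 0.60 × 0.40/2)]² / 0.30² = 41.7,

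which rounds up to 42. So 42 + 84 = 126, with power 90.2%. Then 126 + 18 + 33 = 177, and 177 × 2/3 = 118. The power step and the sums are right.

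**2. Who can count toward the exposure target.** An IgPro20 subject can have 24 + 28 = 52 weeks. A placebo subject can have at most 28 weeks (28 × 7 = 196 days). Only the 118 are eligible.

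**3. Expected number at 20% dropout.** 118 × (1 − 0.20) = 94.4. Applying dropout to everyone first gives the same: 177 × 0.80 × 2/3 = 94.4.

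**4. Chance of meeting the target with 118.** Treat the number retained as binomial, with each subject retained independently.

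| Dropout | Expected retained of 118 | P(at least 101 retained) |
|---|---|---|
| 20% | 94.4 | 7.6% |
| 15% | 100.3 | 49% |
| 14% | 101.5 | 61% |
| 10% | 106.2 | 95% |

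**5. What an expected 101 requires.** With 118 subjects, dropout must be at most 1 − 101/118 = 14.4%. At 20% dropout, 101/0.80 = 126.25, so 127 on IgPro20. At 2:1 that is 127:64, or 191 in total (192 if the total must be a multiple of 3), which is 14 to 15 more than 177. This makes the target expected, not ensured.

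**6. Could another inflation method explain 118?** Multiplying by 1.2 instead of dividing by 0.8 gives 100 × 1.2 = 120, close to 118 but not equal to it. Undoing that step, 118/1.2 = 98.3, which is still below the target.

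**7. Duration.** 52 × 7 = 364 days of planned treatment. The Schedule of Activities shows no study drug at the Day 365 end-of-treatment visit.

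**The case against.** The best defence is the continuation rule. At the 20% dropout used here, the 10% threshold is passed and randomization goes on. The protocol also calls 177 approximate (synopsis and 4.1). On this view 118 is not a ceiling, and both 94 and 7.6% hold only if randomization stops at 177. That condition is correct and has to be stated. It does not rescue the sentence. The rule says nothing about how many more subjects, up to what limit or toward what exposure count, and it sits awkwardly with the no-replacement policy in Protocol 7.4. The text also presents 177 as the number reached after allowing for 20% dropout. If continued randomization is needed to pass 100, 177 does not do what is claimed.

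Reading the dropout rate as only approximate does not help either: even at 15% the chance of keeping at least 101 is about one half.

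A reader might also infer from the 364-day schedule that no subject could be treated for more than a year. The documents do not support that. Visits carry a ±3-day window, and SAP 8.2.5 starts each study week at the first infusion actually recorded, so a few subjects could pass 365 days. The duration point is therefore one of wording.

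Finally, the consequences are limited. The exposure count is not an endpoint, an analysis set or a decision rule. SAP Sections 3 and 5 report termination with 16 of 177 randomized and restrict the analyses to descriptive ones. This stands, and it lowers the severity.

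**Conclusion.** The exposure justification for 177 (118:59) is arithmetically wrong in the synopsis, Protocol 9.2 and SAP 4.5. If randomization stops at 177 and dropout is 20%, about 94 subjects complete the 52-week IgPro20 course, roughly 7 short of the 101 needed, and the target is met with probability 7.6%. This rests on 20% dropout applying equally to the IgPro20 arm and, for the probability, on independent dropout between subjects.

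Whether continued randomization would have closed the gap cannot be determined from the documents, because the rule is not quantified.

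It would be wrong to infer that the trial was underpowered. The 126 reproduces, 177 exceeds it, and the primary test and alpha are untouched. Severity is minor to moderate: the error is certain, but no planned result changes.

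**What to change.** Restate the sentence in Protocol 1.1, Protocol 9.2 and SAP 4.5 along these lines: *177 (118:59) is expected to give about 94 subjects with 52 weeks of IgPro20 at 20% dropout if randomization stops at 177; more than 100 is expected only if dropout is about 14% or lower, or if randomization is continued.* This also replaces the more-than-1-year wording with 52 weeks.

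In the same edit, reconcile the sentence with the continuation rule (how many more subjects, up to what limit and for which target) and with Protocol 7.4. Whether to keep a target above 100, at about 191 subjects under 20% dropout, or to lower it is the sponsor's choice.

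The clinical study report needs at most a note that the planned exposure rationale was inconsistent. A forecast for 177 subjects has no place there after 16 were randomized.

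The cost is one sentence in three places and a clarified rule. No analysis changes.

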### **9.3. Analysis Sets**

All decisions regarding definition of analyses sets will be made prior to unblinding.

#### **9.3.1. Screened Analysis Set**

The Screened Analysis Set consists of all subjects who provided written informed consent.

#### **9.3.2. Intention-to-Treat Analysis Set**

The Intention-to-Treat (ITT) analysis set consists of all subjects in the Screened Analysis Set who were randomized into the study. This analysis set will be analyzed using the treatment to which the subject was randomized regardless of the treatment actually received.

#### **9.3.3. Per-Protocol Analysis Set**

The Per-protocol (PP) set will consist of all subjects who satisfy the ITT criteria and have no major protocol deviations that impact the primary efficacy endpoint (as defined in the SAP).

Subjects in the PP set will be analyzed using the ITT principle (ie, according to randomized treatment assignment).

#### **9.3.4. Safety Analysis Set**

The Safety Analysis Set consists of all subjects in the ITT Analysis Set who received any IMP. The Safety Analysis Set will be analyzed using the treatment that the subject actually received.

#### **9.3.5. Pharmacokinetic Analysis Set**

The PK Analysis Set consists of all subjects in the Safety Analysis Set with at least 1 quantifiable PK concentration of IgG after administration.

The PK Substudy Analysis Set includes all subjects in the Safety Analysis Set who enrolled into the PK Substudy and have intensive concentration data to provide interpretable results for the specific parameters of interest for IgG.

## 9.4. Statistical Analyses and Methods

The SAP will include a more technical and detailed description of the statistical analyses described in this section. This section is a summary of the planned statistical analyses of the most important endpoints.

### 9.4.1. General Considerations

All statistical tests will be 2-sided and will be performed at the 5% level of significance, unless otherwise stated.

In general, continuous variables will be summarized using descriptive statistics (number of observations [n], mean, standard deviation [SD], median, minimum, and maximum). Categorical variables will be summarized using frequencies and percentages. For repeated observations of continuous variables, change from baseline will also be summarized. Summary statistics will be described separately for each treatment group.

Baseline refers to the last measurement or the last calculated value before the first administration of IgPro20. For COMPASS-31, the assessment at the Screening visit will be used as baseline value (for total as well for all domains).

Missing dates / times in AE and concomitant therapies data will be handled as described in the SAP. There will be no imputation schemes applied to missing data unless otherwise specified in the SAP. Values that are below the limit of quantification in the PK data will be handled as described in the SAP.

### 9.4.2. Efficacy Analyses

All efficacy analyses will be conducted using the ITT Analysis Set except otherwise. The details of all analyses, as well as by visit analysis, will be defined in the SAP.

#### 9.4.2.1. Primary Estimand and Analysis of Primary Efficacy Endpoint

The subject's response status of no longer meeting diagnostic criteria of post-COVID POTS as measured by standardized standing test (ie, no longer experiencing HR increase of  $\geq 30$  bpm, in the absence of 20 mmHg decrease of HR [orthostatic hypotension]) will be assessed as the primary endpoint.

A subject is considered a responder if

$$\begin{aligned} \text{HR}_{\text{W25,10min}} - \text{HR}_{\text{W25,0min}} &< 30 \text{ bpm} \quad \text{and} \\ \text{BP}_{\text{W25,as}} - \text{BP}_{\text{W25,bs}} &> -20 \text{ mmHg} \end{aligned}$$

Where,  $\text{HR}_{\text{W25,10min}}$  indicates the average of the 2 highest HR measures (bpm) within 10 minutes after start of the standing test at W25,  $\text{HR}_{\text{W25,0min}}$  indicates the HR measure (bpm) at start of the standing test at W25,  $\text{BP}_{\text{W25,as}}$  indicates the systolic blood pressure measure (mmHg) at any time point within 10 minutes after start of the standing test at W25, and  $\text{BP}_{\text{W25,bs}}$  indicates the systolic blood pressure measure at the start of the standing test at W25.

Consequently, a subject is considered a non-responder, if

$$\begin{aligned} \text{HR}_{\text{W25,10min}} - \text{HR}_{\text{W25,0min}} &\geq 30 \text{ bpm} \quad \text{or} \\ \text{BP}_{\text{W25,as}} - \text{BP}_{\text{W25,bs}} &\leq -20 \text{ mmHg} \end{aligned}$$

Response rates [%] will be determined for placebo and IgPro20.

For each treatment group point estimates and 95% Wilson Score confidence intervals will be provided, for the difference between treatment groups (IgPro20 – placebo) the point estimate, 95% Farrington-Manning confidence interval and 1-sided p-value will be provided.

To show the magnitude of the HR increase at baseline ( $HR_{10min, baseline} - HR_{0min, baseline}$ ) and at W25 ( $HR_{10min, W25} - HR_{0min, W25}$ ), the proportion of subjects within the following categories will be analyzed. This analysis will show the proportion of the subjects with normal HR increase after the standing test at the end of the treatment period.

- HR increase < 10 bpm
- $10 \text{ bpm} \geq \text{HR increase} < 15 \text{ bpm}$
- $15 \text{ bpm} \geq \text{HR increase} < 20 \text{ bpm}$
- $20 \text{ bpm} \geq \text{HR increase} < 25 \text{ bpm}$
- $25 \text{ bpm} \geq \text{HR increase} < 30 \text{ bpm}$
- $30 \text{ bpm} \geq \text{HR increase} < 35 \text{ bpm}$
- $35 \text{ bpm} \geq \text{HR increase} < 40 \text{ bpm}$
- $40 \text{ bpm} \geq \text{HR increase} < 45 \text{ bpm}$
- $45 \text{ bpm} \geq \text{HR increase} < 50 \text{ bpm}$
- HR increase  $\geq 50 \text{ bpm}$

#### 9.4.2.1.1. Detail of Primary Estimand

The primary comparison of interest is to quantify the treatment effect of IgPro20 versus placebo. The treatment effect of interest is the difference in the proportion of subjects no longer meeting diagnostic criteria of post-COVID POTS as measured by standardized standing test (no longer experiencing HR increase of  $\geq 30 \text{ bpm}$  in the absence of 20 mmHg decrease of SBP [orthostatic hypotension]).

The attributes of the primary estimand, as defined in the ICH E9(R1) guidance, are provided in Table 5.

